Title of study

Wearable Monitoring Systems for Swallowing Function and Disorders

NCT #

NCT04243577

Latest Approval Date

10/18/2023

Study Protocol & Statistical Analysis Plan

STUDY PROTOCOL

Objective

Wearable tele-rehabilitation technology allows for the efficient provision of rehabilitation services from a distance, facilitating tele-management of many disorders. The proposed research aimed to develop and validate a mechanically compliant, easy-to-use, and inexpensive wearable tele-monitoring system, for future use in the rehabilitation of swallowing disorders (dysphagia). The hypothesis was that the newly developed surface electromyographic (sEMG) wearable sensors would have equal or better performance than traditional wired sEMG sensors used today in clinical practice. Factors related to signal quality and patient reported outcomes (e.g., satisfaction/comfort level, adverse effects etc.) were examined.

Design and Devices

This study is a within subject randomized cross-over design study. Two iterations of a wearable surface EMG sensors patch we developed were tested against commercially available wired devices. The first iteration of the wearable sensor patch was an ultrathin patch with a honeycomb-inspired design that included sEMG and strain sensors in order to capture muscle activity and thyroid movement signals from the submental area during swallows and swallow maneuvers/exercises. The second iteration was a more durable slightly thicker flexible, non-stretchable, and double-sided thin patch. The exact same methods were used to test both iterations against commercially available conventional sensors. For both iterations' testing, the order of the experimental conditions differed across groups. Group A participants completed the experimental protocol with the conventional electrodes first, and Group B participants completed the protocol with the experimental patch first. There was a 10-min rest period between the two experimental conditions.

The first iteration testing was completed in 40 healthy older adults. Results revealed technical improvements were needed and therefore a second improved version of the sensor was then developed. The second iteration testing was done in an additional sample of 30 healthy older adults. A total of 70 healthy older participants were included in the study.

Methods

Participants

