Healthy older adults 50-85 years old (the typical age range of our target clinical population for future studies) were recruited in this study. Inclusion criteria were: 1) no history of dysphagia, 2) no history of neurological disease, head/neck cancer, radiation or surgery, 3) a score in the normal/mild range on the Montreal Cognitive Assessment (MoCA), and 4) a score of <3 on the Eating Assessment Tool (EAT-10; a self-report screening for dysphagia). Exclusion criteria were: 1) history of dysphagia; 2) history of neurological disease, head/neck cancer, radiation or surgery, 3) a score in moderate-severe range on MoCA, and 4) a score of >2 on the EAT-10.

Instrumentation Validation – Data Collection

For each iteration of the device, a group of participants was tested using the experimental device/sensors and the commercially available ones in counterbalanced order. Results were analyzed to allow design improvements before the next iteration was developed and tested. To validate each of the two iterations of the newly developed sEMG patch, we used wired electrodes (e.g., AED Brands, A snap-style pad) connected to a commercially available wireless amplifier (BioRadio, GLNeuroTech Inc.), as the comparison system. During this experiment, the electrodes were placed on the submental muscles (under the chin). The sEMG signals were sampled while subjects remained as still as possible and sat upright with the head in neutral

position. Participants were asked to complete several types of swallows multiple times. Each set of tasks was tested with one type of device first (conventional or experimental) and was repeated 10 min after the first set with the other type of device. For both types of devices, swallows were confirmed via a nasal airflow cannula to detect the swallow apnea (nasal airflow cessation), and an observer's button that was be pressed at swallow completion.

Outcome Measures and Data Analysis

Primary Outcome Variables – Signal Quality parameters

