The study was designed to have at least 80% power to detect a difference in the primary variables of interest, that is, SNR, and normalized mean amplitude of swallow trials. The sample size was determined via a power analysis based on pilot results. Alpha level was set to .025 to correct for multiple comparisons. Quantile-quantile plots and the Shapiro-Wilk test was also used to assess normality. For S/N ratio comparisons non-inferiority tests were used for both iterations' testing. For the normalized amplitude data, equivalency testing was used for both iterations' testing. Margins for these tests were calculated using our preliminary data acquired with the conventional electrodes, which were considered as the current gold standard. Descriptive statistics (frequency counts) were used to report adverse effects (skin related effects). Paired t tests were used to test for differences in satisfaction/comfort level.

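### Device order is randomised in a two-period crossover, but no analysis in the SAP uses it: comfort is a plain paired t test, and the S/N and amplitude tests have no stated model

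*Combined protocol and SAP*

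**What the plan says.** Under Design and Devices the protocol states: "This study is a within subject randomized cross-over design study". There are two orders. "Group A participants completed the experimental protocol with the conventional electrodes first", and Group B began with the patch. "There was a 10-min rest period between the two experimental conditions". The data-collection section says the experimental sensors and the commercial ones were tested in each iteration with the "commercially available ones in counterbalanced order", and that each task set was "repeated 10 min after the first set with the other type of device". Electrodes were on the submental muscles. Iteration 1 had 40 participants and iteration 2 had 30.

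The Statistical Analysis Plan is one paragraph. Its inferential statements on outcomes are these:

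- S/N ratio: "For S/N ratio comparisons non-inferiority tests were used" for both iterations.
- Normalised amplitude: "For the normalized amplitude data, equivalency testing was used" for both iterations.
- Comfort: "Paired t tests were used to test for differences in satisfaction/comfort level".

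Skin effects are reported as counts. The SAP does not mention group, order, sequence, period or carryover. It gives no model or test statistic for the S/N and amplitude comparisons, and the sizes of Groups A and B appear nowhere.

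**The concern.** Each participant performs the same swallow tasks twice in one session, with the same muscle group. A shift between the first and second set, for example from practice, fatigue or familiarity, is plausible, although the documents report none. Randomising the order makes such a shift estimable and removable. An analysis that ignores order does neither.

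This matters here because non-inferiority and equivalence are both decided by where confidence limits fall against a margin. With equal order groups, an ignored period change only widens the interval: a positive conclusion stands, but a patch that truly meets the margin is more likely to miss it. With unequal groups, part of the period change also leaks into the device estimate and can push it either way. A main effect of order group itself cancels from within-person differences and is not at issue.

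**Working it through.** **Inputs from the documents.** n = 40 and n = 30; power of at least 80%; alpha .025, with sidedness not stated; two orders, 10 minutes apart.

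**Not in the documents, so assumed.** The SD of the paired difference, the numerical margins, the Group A/B sizes and the size of any period change. Alpha .025 is applied to each one-sided test. The calculations are conditional on the signal tests being simple paired comparisons.

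**The plan's own figure.** The 80% power cannot be reproduced without an SD or a margin. The margins that would give 80% power with no period change, in SDs of the paired difference, are:

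| n | Non-inferiority margin | Equivalence margin |
|---|---|---|
| 40 | 0.455 | 0.526 |
| 30 | 0.529 | 0.612 |

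**Structure.** Let D be patch minus conventional for one person, with true device difference δ and period change p (second set minus first).

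- Group A (conventional first): D = δ + p + error
- Group B (patch first): D = δ − p + error
- The simple paired mean estimates δ + p(nA − nB)/n
- The average of the two group means estimates δ whatever p is

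Write r for p in SDs of the paired difference.

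**Equal groups.** There is no bias. The SD used by the paired test is inflated by √(1 + r²·n/(n − 1)). For n = 30 and r = 0.5 this is √(1 + 0.25 × 30/29) = 1.12. The equivalent sample size is about n/(1 + r²): at r = 0.5, 30/1.25 = 24 and 40/1.25 = 32. Simulated power at δ = 0, n = 30 and n = 40 together:

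| r | Interval wider by | Non-inferiority power, no period term | Equivalence power, no period term |
|---|---|---|---|
| 0 | 0 | 80% | 80% |
| 0.1 | 0.5% | about 80% | about 80% |
| 0.25 | 3% | 78% | 78% |
| 0.5 | 12% | 72–73% | 70% |
| 1.0 | 42–43% | 50% | 34–35% |

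With a period term (mean of the two group means, pooled within-group SD, n − 2 df), power stays at about 80% in every row. At r = 0 the term costs at most 0.2 points. Without it, non-inferiority type I error falls to about .022 at r = 0.25 and .014 at r = 0.5, which is conservative.

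**Unequal groups.** The splits are assumed, and the leak is taken in the direction that favours the patch. Leak = r(nA − nB)/n.

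| Split | Leak | At r = 0.25 / 0.5 (SD) | Non-inferiority type I error, no period term |
|---|---|---|---|
| 16/14 | 2/30 = 0.067r | 0.017 / 0.033 | at most .027 |
| 21/19 | 2/40 = 0.05r | 0.013 / 0.025 | at most .027 |
| 17/13 | 4/30 = 0.133r | 0.033 / 0.067 | about .033 at both |
| 22/18 | 4/40 = 0.10r | 0.025 / 0.05 | .030–.032 |
| 60:40 | 0.20r | 0.05 / 0.10 | about .04 at r = 0.25; about .05 (n = 30) or .056–.059 (n = 40) at r = 0.5 |

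For 17/13 the leak is 0.033/0.529 = 6% and 0.067/0.529 = 13% of the non-inferiority margin. The period-adjusted test stays at about .024–.026 throughout. At 60:40 with r = 0, adjustment costs about 2 points of power.

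**The case against.** The strongest reply is that order is already handled by design. Counterbalancing normally aims at equal groups, 40 and 30 split evenly, and nothing in the text points to imbalance. With equal groups the device estimate is unbiased and the test is conservative, so a positive finding is safe. A type I problem needs four things together: an unadjusted analysis, unequal groups, a real period change, and the direction that favours the patch. None is documented. For the signal outcomes the SAP is silent, which does not show that order was ignored in the analysis as run. Loss of power becomes material only at period changes of about 0.5 SD or more, which the documents do not support. If the pilot SD came from mixed-order pairs, the planned power may already absorb part of the loss.

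Most of this stands, and it limits the point to a modest one; the type I scenario is a contingency. It does not remove the point. Counterbalancing prevents bias only when the groups are equal, and it does not take period variance out of the interval. For comfort the test without a period term is stated outright.

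It is also fair to say that a sequence term is not needed when both periods are complete. Including it is conventional and leaves the device estimate unchanged. Finally, a period term does not deal with carryover; the 10-minute rest is the only provision for that, and its length is not justified.

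**Conclusion.** The concern holds. The trial randomises device order, and the SAP uses it in no stated analysis: explicitly so for comfort, and by leaving the model unspecified for S/N and amplitude.

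The size is conditional on a simple paired analysis and on margins back-solved to 80% power. With equal groups the consequence is lost precision only: about 2 points of power at a period change of 0.25 SD, and 7–10 points at 0.5 SD. With unequal groups, non-inferiority type I error can rise above .025: to about .03 for 17/13 or 22/18, and barely at all for 16/14 or 21/19. No stated figure is shown to be wrong, and a positive result from equal groups is not undermined. The change should be made because it uses information the design already provides, at almost no cost.

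**What to change.** For each iteration, analyse amplitude, S/N ratio and comfort with a two-period crossover analysis: device and period as fixed effects, sequence included by convention, participant random. The standard two-period crossover t method is an alternative. Take the non-inferiority limit and the equivalence limits from the device term, and put this model in the SAP in place of the unspecified tests and the paired t test.

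Report the Group A and Group B sizes in each iteration and the estimated period effect with its interval. Discuss carryover separately: say whether effects of the first set could persist at the same site after 10 minutes, since the period term will not remove them.

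The cost is one degree of freedom, a few sentences of SAP text, and a re-analysis. Both iterations are described as completed, so no new data are needed.

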Signal quality outcomes tested across both iterations' tests included normalized task-related EMG amplitude (primary outcome), and signal to noise (S/N) ratio. Because task sEMG amplitudes vary among subjects (e.g., as a function of electrode impedance), we expressed amplitude in microvolts and normalized these values within subjects. For normalization, participants produce 3 trials of maximum lingual press, and we expressed the task-related EMG amplitudes as percentages of the amplitude of this criterion gesture. For analysis, research assistants blinded to sensor type conducted analyses using a custom MATLAB script.

Secondary Outcome Variables – Preclinical parameters

We examined adverse effects and safety by thoroughly inspecting participants' submandibular skin before and after each experiment. Specifically, we documented the incidence of skin irritations in the subjects. A visual inspection form including a binary scale (YES/NO) was devised by the investigators (no formal name) and was used by a rater who thoroughly inspected the participants' submandibular skin before and after each experiment. For any irritation or change in appearance YES was selected and the type of irritation was descriptively recorded (e.g., red skin). This form was completed by a rater who was not part of the data collection process and who was blinded to sensors type to avoid any bias. The number of YESs were used to calculate the incidence of these adverse effects in the sample. This inspection was completed immediately after removal of each sensor type and 5 minutes later as well.

Ease-of-use/comfort was examined using a survey (using a positive centered 5-point Likert scale) with questions about ease-of-use/comfort after each experiment with each device. This survey included statements related to the participants' ease-of-use/comfort during the experimental protocol (e.g., I was comfortable while the experimenter placed the sensors on my skin). The answers were rated on a 10-point scale (i.e., 1 = extremely uncomfortable, 10 = extremely comfortable). Higher values indicated better or higher satisfaction/ comfort scores. Total scores were compared across conditions/devices tested.

STATISTICAL ANALYSIS PLAN

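### Skin effects, the only safety outcome described, are reported as bare frequency counts, with no interval and no stated patch-versus-wired contrast, although each participant wore both sensors

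*Combined protocol and SAP*

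**What the plan says.** The Objective hypothesises that the new sensors "would have equal or better performance than traditional wired sEMG sensors used today in clinical practice". The sentence after it adds: "Factors related to signal quality and patient reported outcomes (e.g., satisfaction/comfort level, adverse effects etc.) were examined".

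Design and Devices sets out the structure: "This study is a within subject randomized cross-over design study". Each participant was tested with a patch and with the wired sensors, with 10 minutes of rest between. Two patch versions were used. For the first, an ultrathin honeycomb design, "The first iteration testing was completed in 40 healthy older adults". For the second, which was thicker, non-stretchable and double-sided, "The second iteration testing was done in an additional sample of 30 healthy older adults". The total is given as 70.

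Under Secondary Outcome Variables – Preclinical parameters: "We examined adverse effects and safety by thoroughly inspecting participants' submandibular skin before and after each experiment". The form is YES/NO. The rater was outside the data collection and blinded to sensor type. Skin was inspected immediately after each sensor type was removed and again 5 minutes later. The summary measure is described as follows: "The number of YESs were used to calculate the incidence of these adverse effects in the sample".

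The Statistical Analysis Plan assigns non-inferiority tests to S/N ratio, equivalence tests to normalized amplitude and paired t tests to comfort. For skin effects its whole provision is: "Descriptive statistics (frequency counts) were used to report adverse effects (skin related effects".

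**The concern.** The data collection supports a comparison, but the analysis plan does not state one. Inspecting after each sensor with a blinded rater is useful mainly for setting one sensor against the other, and the crossover supplies matched pairs. A list of counts uses neither feature and does not show how much irritation the data leave possible.

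The denominator is also unclear. The tests of S/N ratio and amplitude are specified for both iterations, whereas the skin sentence mentions neither iteration nor sensor. The two patches are different materials against the skin, so a count over all 70 participants would not describe the final patch.

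What is at stake is how far any statement on skin safety can go for a device meant for later use in dysphagia rehabilitation. The primary signal-quality results are not affected.

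**Working it through.** **The plan's own figure.** There is none to reproduce. The stated power of at least 80% covers S/N ratio and normalized amplitude only. No rate, margin or interval is given for skin effects, and the documents report no event data, so the counts below are illustrations.

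**Inputs.** n = 30 for the final patch, n = 40 for the first patch and 70 in total (Design and Devices). The outcome is taken as binary per participant.

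**Step 1: exact limits for one sensor.** With zero events the Clopper-Pearson two-sided 95% upper limit is 1 − 0.025^(1/n):

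- n = 30: 1 − 0.025^(1/30) = 11.6%
- n = 40: 1 − 0.025^(1/40) = 8.8%
- n = 70: 1 − 0.025^(1/70) = 5.1%

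With x events the limits are beta quantiles: lower B(0.025; x, n − x + 1) and upper B(0.975; x + 1, n − x).

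| Events in 30 | Exact two-sided 95% interval |
|---|---|
| 0 | 0% to 11.6% |
| 1 | 0.1% to 17.2% |
| 2 | 0.8% to 22.1% |

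**Step 2: chance of a clean result.** P(0 events) = (1 − p)^30. The values of p are assumed, because the documents give no rate.

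- p = 2%: 0.98^30 = 54.5%
- p = 5%: 0.95^30 = 21.5%
- p = 10%: 0.90^30 = 4.2%

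**Step 3: the within-person difference.** Suppose no one in the second iteration reacts to either sensor. With no discordant pairs, the Tango score upper limit for patch minus wired solves n·d / √(n·d·(1 − d)) = z, so d = z²/(n + z²). With z = 1.96 and n = 30, d = 3.84/33.84 = 11.4%. Even an entirely clean paired table leaves an excess of about that size open.

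**Step 4: effect of the denominator.** If the sample were read as all 70 participants, a zero count would carry a limit of 5.1%. The final patch's own limit is 11.6%, and 5.1/11.6 = 0.44, so the pooled limit would be less than half of it. This step depends on that reading.

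**The case against.** The strongest reply is that descriptive reporting of a secondary, unpowered safety outcome is a defensible choice in a small validation study in healthy volunteers. That stands. A formal test would add little: exact McNemar needs six discordant participants, all in one direction, to fall below 0.05 (2 × 0.5^6 = 0.031, against 2 × 0.5^5 = 0.063 for five). Neither a test nor more power is asked for. Anyone can compute an interval from a published count and its denominator, but only if the count is given per participant, per sensor and per iteration, which the text does not promise.

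Counts by sensor are compatible with the wording, and the blinding hints at them. The gap is therefore an unstated contrast, not one that is ruled out.

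On pooling, the second group is itself called an additional sample, and Instrumentation Validation – Data Collection describes analysis between iterations. No passage proposes a single incidence over 70. The wording is ambiguous, and the 5.1% figure is conditional on one reading of it.

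A raw paired table also has a weakness. Both sensors go on the submental area about 10 minutes apart, so redness from the first could still be visible after the second. This is a fair criticism, and it is why the fix counts new irritation and shows the results by order.

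A reader might infer two stronger claims. The first is that adverse effects are explicitly part of the equal-or-better hypothesis. The documents do not say so: that sentence concerns performance, which is undefined, and adverse effects follow in a separate sentence as something examined. The second is that a low count would be accepted as evidence of safety. The documents set no safety criterion and draw no such conclusion.

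**Conclusion.** The point holds as a gap in precision and comparison. Skin effects are the only safety outcome described, and paired, blinded observations were collected. The plan commits only to frequency counts, without an interval, a stated patch-versus-wired contrast or a clear denominator.

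For the 30 users of the final patch, a count of zero is compatible with a true rate up to 11.6%, and a count of one with rates from 0.1% to 17.2%. A patch that irritates 5% of users would show no events about one time in five. These figures assume one binary outcome per participant and independent participants. The counts and the 5% rate are illustrative.

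This is an inexpensive improvement to reporting. It does not show that the descriptive approach is wrong, that pooling was planned or that a safety claim was made.

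**What to change.** Replace the skin-effects sentence in the Statistical Analysis Plan with the following:

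- For each iteration and each sensor, report the number of participants with new irritation relative to the inspection before that sensor, with an exact Clopper-Pearson 95% interval.
- For each iteration, give the paired 2x2 counts (patch only, wired only, both, neither) and the within-person difference with a 95% interval, for example the Tango score interval.
- Show these also by sensor order, because the second sensor goes on the same area 10 minutes later.
- State that the two patch versions are not combined, and clarify which participants form the sample for incidence.
- Limit any statement on skin safety to what the interval excludes.

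This needs no hypothesis test, no added power and no new participants. It does assume that the records identify the participant, the sensor and the inspection, including one before the second sensor. If that inspection was not made separately, the one 5 minutes after removal of the first sensor is the nearest substitute, and the report should say so.

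The cost is a few lines of SAP text, one small table and a less favourable safety statement than a bare count would suggest.
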